If onsite monitoring visit(s) are deemed appropriate by the Sponsor, the Investigator will permit representatives of the Sponsor’s monitoring team to have direct access to inspect all source data/documents, study

documents/binders, study subject case report forms, corresponding sections of study subject medical/hospital records, and any other documents relevant to the study. All Sponsor visits (including site initiation) will be documented using the **Site Monitoring Visit Log** (Appendix C).

X. Risk Analysis

This post-market clinical study is classified as minimal risk and there are no anticipated risks specific to study participation other than the potential loss of confidentiality. There are no experimental procedures in this study, and participation in this study is not anticipated to affect the medical treatment of enrolled subjects.

When used in accordance with product labeling, the risks associated with the use of N-Force Screws augmented with N-Force Blue are similar to those of standard intracapsular femur fracture treatment systems used for the same clinical indication or purpose. These risks are categorized below as either general surgical risks or risks associated with the intracapsular femur fracture procedure/study device. Unanticipated adverse events can also occur.

For general surgical risks, please refer to the FDA cleared instructions for use for this product.

XI. Statistical Considerations

Data collected in this study will be summarized descriptively and descriptive summaries will be the basis of any study reports issued. These summaries may be used for interim study reports and may also be used to support regulatory submissions, presentations, and/or publications. Additional surgical technique and instrumentation data may be collected and evaluated.

A. General Statistical Methods

Statistical methodology will consist of summarizing collected data descriptively. Categorical data (e.g., gender or race) will be summarized using counts and percentages, and 95% Confidence Interval (CI), over the time periods of interest. Continuous data, such as age, will be summarized by using means, medians, standard deviation, minimum, maximum, and 95% CI over the time periods of interest.

B. Sample Size

Using an observed historical control performance reoperation rate of ~15% ^{[4][7]},

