for intracapsular femur fractures, 151 evaluable subjects will be required at 12 months follow-up to show necessary statistical improvement from the historical revision rate. With an expected lost to follow-up rate of 20%, 190 subjects will be required for this clinical study. The assumed reoperation rate for the N-Force Screws augmented with N-Force Blue is 7.5%.

XII. Quality Control & Quality Assurance

The study is conducted in accordance with the Declaration of Helsinki and the ISO 14155:2011.

The Investigator will be required to permit representative(s) of the Sponsor's monitoring team to inspect all Case Report Forms and corresponding sections of the study patients office records and/or hospital original medical records. These audits will be done for quality assurance purposes, i.e. verifying adherence to the Clinical Investigation Plan and the completeness and accuracy of the data being entered on the Case Report Forms.

The Clinical Investigation Plan will be provided to all participating study centers. The Investigators will be fully trained in the proper reporting and submission of trial data prior to patient enrolment. Completed Case Report Forms will be reviewed before entering the data into a central database by the Sponsor.

The Clinical Study Manager is responsible for generating data queries for missing or unclear data if needed. It is the responsibility of the Clinical Study Manager to ensure data quality.

There are regular meetings between the Investigators and Zimmer Biomet Clinical Affairs staff. Written correspondence to all sites is used to inform the Investigators of routine study details and to update them on study status.

XIII. Suspension or Premature Termination of the Clinical Investigation¹

Sponsor may suspend or prematurely terminate clinical investigation site(s) or entire clinical investigation for significant and documented reasons. If suspension or premature termination occurs at an individual investigation site, sponsor shall inform the responsible regulatory authority(s) as appropriate and ensure that ethic committee(s) are notified. If the suspension or premature termination was in the interest of safety, the sponsor shall inform all other principal investigators. If suspension or premature termination occurs,

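### Functional and quality-of-life scores are summarised as raw visit means despite 20% expected loss; the 12-month means are too favourable if poorer recoverers are lost more often

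*Combined protocol and SAP*

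**What the plan says.** Section XI.A is the whole analysis plan for continuous data. It opens with "Statistical methodology will consist of summarizing collected data descriptively", and such data are then to be "summarized by using means, medians, standard deviation, minimum, maximum, and 95% CI over the time periods of interest". The section does not name the four scores, but no other method in the document could apply to them.

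Section IV lists Harris Hip Score, Timed Up-And-Go, FIX-IT and EQ-5D-5L as secondary endpoints. The Data Collection Overview (Section II) schedules each at 6 weeks and at 3, 6 and 12 months, and none before surgery.

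On missing subjects, Section XI.B says "With an expected lost to follow-up rate of 20%, 190 subjects will be required for this clinical study" and that "151 evaluable subjects will be required at 12 months follow-up". Sections VIII.L, IX.D.6 and XII add counselling, documented contact attempts and data queries. These are conduct measures. The document contains no missing-data method, repeated-measures analysis, imputation or sensitivity analysis, and no comparison of completers with dropouts.

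Sections VIII.K, IX.D.3 and IX.D.8 end participation at death and at removal of a study device, including removal of a single screw.

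**The concern.** Summarising collected data visit by visit means that each mean describes whoever was measured at that visit. With 20% lost by 12 months, the 6-week and 12-month means refer to different sets of people. A dropout's earlier scores enter their own visit's summary but do not inform the 12-month estimate.

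If people who recover poorly are lost more often, two things follow. A reader who compares visits will take some attrition for recovery. The 12-month 95% interval will also be centred too favourably for the implanted population (for Timed Up-And-Go, a mean time that is too short). There is no concurrent arm in which similar attrition could partly cancel the bias. Section XI allows these summaries to be used in regulatory submissions and publications.

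**Working it through.** **1. The plan's own figures.** Inputs from Section XI.B: historical reoperation rate p0 = 0.15, assumed rate p1 = 0.075. Alpha and power are not stated; two-sided 0.05 and 80% are assumed here because they return the stated number.

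n = [(1.96·√(0.15·0.85) + 0.842·√(0.075·0.925)) / 0.075]² = 151.0, matching 151.

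Allowing for loss: 151/0.80 = 188.75, so 189 against the stated 190. Conversely, 190·0.80 = 152 subjects observed at 12 months. The 20% therefore enters the plan only as an inflation of enrolment.

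**2. Bias from a given gap.** Let m be the share missing and d the gap, in SD, between the mean scores of observed and missing subjects. The documents give no SDs or gaps, so d is an assumption with range 0 to 1.

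Bias of the raw mean = m·d. SE = 1/√152 = 0.081 SD, t = 1.976, half-width 0.16 SD.
Coverage = Φ(t − bias/SE) − Φ(−t − bias/SE).

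| Gap d (SD) | Bias, m = 0.20 (SD) | Coverage of nominal 95% CI |
|---|---|---|
| 0 | 0 | 95% |
| 0.25 | 0.05 | 91% |
| 0.50 | 0.10 | 77% |
| 0.75 | 0.15 | 55% |
| 1.00 | 0.20 | 31% |

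**3. Dropout driven by the last observed score.** Simulation with 190 subjects, four visits, multivariate normal scores and 20% missing at 12 months. Dropout is logistic with slope 0.5 or 1.0 per SD worse score, so odds ratios are e^0.5 = 1.6 and e^1.0 = 2.7. All settings are assumptions.

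| Correlation | Slope | Raw bias (SD) | Coverage |
|---|---|---|---|
| 0.5 | 0.5 | 0.051 | 90% |
| 0.5 | 1.0 | 0.092 | 80% |
| 0.7 | 0.5 | 0.070 | 86% |
| 0.7 | 1.0 | 0.133 | 59% |

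Repeat runs gave 0.05 to 0.14 SD. A likelihood-based mean that uses all visits had bias below 0.005 SD and no larger standard error. That result is expected, because this mechanism is the one under which such a model is valid.

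**4. Dropout driven by the unseen score.** Same set-up, but loss depends on the score that is never recorded. Raw bias is 0.07 to 0.16 SD, and the model reduces it to 0.03 to 0.07 SD. A simpler version with only one earlier visit (correlation 0.6) is less kind: 0.09 and 0.17 SD fall to 0.06 and 0.12 SD, and coverage rises from 78% and 38% to 87% and 66%.

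**5. Dropout unrelated to recovery.** Raw and model means are both unbiased, with about 95% coverage.

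**The case against.** The strongest case against is that the harm is hypothetical. The documents give no score SD, correlation, attrition pattern or direction of dropout. Well-recovered subjects who skip visits would reverse the bias. These are secondary, descriptive endpoints with no hypothesis, threshold or planned between-visit change, and the sample size rests on reoperation. This stands, and it is why the point is conditional and minor. It does not remove the point, because Section XI.A promises a 95% CI, which is a statement about a population.

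A second objection is that the model's near-zero bias in step 3 is built into the mechanism. This also stands. A reader might infer that a repeated-measures model cures the problem, but step 4 shows a partial correction. With no pre-operative scores scheduled, a subject lost before any post-operative score contributes nothing. Normality is also only an approximation for a timed test and bounded scores.

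A third objection is that a model fitted to every implanted subject would silently extrapolate scores for those who died or had a device removed, as if they had continued. This is correct. A model mean offered without a defined target could be harder to interpret than the raw mean, and the fix has to deal with it.

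**Conclusion.** The plan analyses the four scores as raw means of collected data and meets an expected 20% loss only with extra enrolment. If worse scorers are lost more often, the 12-month means are too favourable by about 0.05 to 0.14 SD and the nominal 95% interval covers about 90% down to 60%. This assumes correlations of 0.5 to 0.7 and dropout odds 1.6 to 2.7 times higher per SD worse score. If loss is unrelated to recovery, the bias is zero.

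A reader might infer that the reported means will be biased. The documents do not support that, since nothing in them shows that loss follows recovery. Exit after device removal is a documented and probably non-random source of missing scores, but it is a question of defining the target and is not the loss to follow-up sized here. The primary endpoint is not affected by this point. Severity is low, and the change is a cheap improvement.

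**What to change.** Keep the raw summaries and add to Section XI.A:

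- **Model.** For each of the four scores, a mixed model for repeated measures with visit as a categorical effect, unstructured covariance and all available post-operative visits, giving the mean and 95% CI at each visit. State which EQ-5D-5L quantity is modelled.
- **Scope.** State that the model addresses loss to follow-up and missed visits only.
- **Death and device removal.** Define the target population for scores after either event. Report these subjects, and those unable to perform the walking test, as separate counts, so that the model mean is not read as applying to them.
- **Disclosure.** Report the number missing and the reasons at each visit. The Study Completion form already records reasons for leaving.
- **Sensitivity.** Add a delta-adjusted analysis that makes missing scores worse by a stated range. With 20% missing, each 0.5 SD of delta moves the mean by 0.20·0.5 = 0.10 SD, so the result is easy to present.

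The cost is a few lines of SAP text and one standard model per score, with no new visits, subjects or data. The downside is that the model relies on missingness depending on observed scores. If it depends on unseen scores, only part of the bias goes, which is why the raw means and the sensitivity analysis should be reported alongside.

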Form Name	Pre-op	Operative & Discharge	6 weeks Post-op (± 14 days)	3 months Post-op (± 30 days)	6 months Post-op (± 60 days)	12 months Post-op (± 90 days)	Revision
Informed Consent	X						
Inclusion/Exclusion Criteria	X						
Demographic Evaluation	X						
Operative & Surgical Device Information		X					
Postoperative Discharge Assessment		X					
Timed "Up and Go" Test			X	X	X	X	
X-rays (A/P and Lateral – Operated Side)	X	X	X	X	X	X	X
EQ-5D-5L			•	•	•	•	
Postoperative Follow-Up			X	X	X	X	
FIX-IT Score			X	X	X	X	
Harris Hip Score			X	X	X	X	
Study Completion		*	*	*	*	*	X
**Adverse Event (Complication)	*	*	*	*	*	*	X
Protocol Deviation	*	*	*	*	*	*	*
Physician Radiographic Assessment (including RUSH)			*♦	*♦	*♦	*♦	*♦
Steinberg Classification						*♦	
Explanted Device		*	*	*	*	*	*

X Completed by Investigator or Designee (required)
 • Completed by Patient
 * Completed by Investigator or Designee (as applicable)
 ♦ Independent radiographic review may be performed by Sponsor's designee if requested by the Sponsor.
 ** If device related Adverse Event occurs, a Product Experience Report (PER) must be completed and forwarded to the sponsor within 7 days of occurrence. Supporting documents must be sent to the sponsor as well and include the Operative Report (index and revision) and Radiographs (immediate post-op, all follow-up visits, and pre-revision).

III. Introduction and Purpose

Intracapsular Proximal Femur Fractures are a common injury especially in the elderly population. Optimal treatment remains controversial. Frequently applied operative treatments include three cannulated screws, sliding hip screw, hemi- and total arthroplasty. AAOS Guidelines for femoral neck fractures in the elderly recommend operative fixation for stable non-displaced fractures and arthroplasty for unstable displaced fractures. In a recent landmark randomized trial including more than one thousand patients comparing sliding hip to cannulated screws, every fifth patient had to be repeated to promote fractures

healing [4]. Reoperation rates of 20% for sliding hip screw and 22% for cannulated screw were found; however, the difference was not statistically significant.

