Zimmer Biomet offers a Hip Screw technology that is capable of delivering a Bone Substitute Material (BSM) to the fracture-implant interface for fixation of fractures of the femoral neck [5][6]. This device allows hard setting BSM to the precise location, providing a multi-dimensional fixation that is critical to reduce the chance of joint collapse and articular fragment displacement and ultimately could reduce the high reoperation rates reported for this kind of injury.

This study will assess the reoperation rates, including revision, and document the clinical and radiographic outcomes of hip fracture patients, utilizing the N-Force Fixation System. Results will be compared to “standard” non-augmented cannulated screw (historic control).

IV. Study Objectives

The objective of this prospective study is to assess safety and performance of N-Force Screws augmented with N-Force Blue applied in intracapsular proximal femur fracture treatment. Further results will be compared to non-augmented standard cannulated screws (historic control).

Safety: Will be assessed by monitoring the frequency and incidence of adverse events (AE), serious adverse events (SAE), adverse device effects (ADE), serious adverse device effects (SADE), and unanticipated serious adverse device effects (USADE) and device deficiencies.

Performance: Will be determined by analyzing the fracture healing (union) rate at 6 weeks, 3 months, 6 months, and 12 months postoperatively.

The primary endpoint of this study is defined as re-operation within 12 months after initial surgery. Reoperation is defined as a second surgery to correct the previous procedure or the complications of a previous surgery. For this study, reoperation will include second surgeries to promote fracture healing, relieve pain, treat infection, or improve function including:

- Removal of the implant prior to fracture healing
- Internal fixation with another implant during revision surgery
- Revision to total hip arthroplasty
- Incision and drainage or other soft tissue procedure due to deep infection at the bone implant interface.

Secondary endpoints of this study include:

- Clinical (FIX-IT) and radiologic (RUSH)^{[8][9]} fracture healing at 6 weeks, 3, 6 and 12 months post-surgery.
- Length of femoral neck ^{1.a.[7]}
- Proportion of patients with avascular necrosis at one year FUP (Steinberg classification)
- Functional Index for Trauma (FIX-IT)^[10]
- Harris Hip Score^[11]
- Timed “Up-And-Go” Test^[12]
- EQ-5D-5L

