with the subject. Patients who have previously received N-Force Screws augmented with N-Force Blue may be enrolled in the study if informed consent occurs prior to the end of the 6 weeks follow-up visit window. This will include retrospective chart review for pre-operative and operative data for patients who meet the inclusion criteria (and do not meet any of the exclusion criteria) and have available surgical data. Patients that meet these requirements will be asked to consent to study participation postoperatively. The consented patients will be followed prospectively at designated follow-up visits if all appropriate Ethics Committee approvals and patient consent is obtained. The post-operative clinical and radiographic evaluations will be conducted at 6 weeks, 3 months, 6 months, and 12 months post-surgery.

Review of radiographs will be completed by the investigators at each clinical follow-up interval to determine the incidence of loss of reduction, implant migration and radiographic evidence of fracture healing. In addition, the Investigator will review radiographs at each clinical follow-up interval to ensure radiographic evidence of adverse events is documented and reported to the IRB or EC and the Sponsor as required. At the Sponsor's discretion, the Sponsor may request copies of these radiographs for independent radiologic review. The Sponsor may request one central reviewer for all radiographs independent of the surgeon and institution.

VI. Study Population

The study population for primary statistical analysis will be comprised of males and females who require intracapsular proximal femur fracture repair and satisfy the inclusion/exclusion criteria outlined in this section of the protocol. In total, one-hundred-and-ninety (190) patients will be enrolled.

In order to avoid potential selection bias, each Investigator will offer study participation to each consecutive eligible patient presenting as a candidate for intracapsular femur fracture repair using the commercially available (FDA cleared) N-Force Screws augmented with N-Force Blue. Eligible candidates who express interest in study participation will be offered Informed Consent. The **Inclusion/Exclusion Criteria** case report form should not be completed until the study-specific consent form has been completed.

1. Inclusion Criteria

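### The 12-month reoperation rate has two unreconciled denominators and no rule for incomplete follow-up; a day-365 time-to-event estimate, specified in advance, would serve better than the percentage in XI.A.

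*Combined protocol and SAP*

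**What the plan says.** All references are to the combined protocol and SAP.

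- **Endpoint (IV, Study Objectives).** "The primary endpoint of this study is defined as re-operation within 12 months after initial surgery". The horizon is fixed and counted from surgery.
- **Method (XI.A).** Categorical data "will be summarized using counts and percentages, and 95% Confidence Interval (CI), over the time periods of interest". The examples are demographic and the primary endpoint is not named. No other method appears anywhere in the document.
- **Benchmark and size (XI.B).** "Using an observed historical control performance reoperation rate of ~15" per cent, with 7.5% assumed for the study device, the plan states that "151 evaluable subjects will be required at 12 months follow-up". It adds: "With an expected lost to follow-up rate of 20%, 190 subjects will be required for this clinical study".
- **Population (VI).** "The study population for primary statistical analysis will be comprised of males and females who require intracapsular proximal femur fracture repair" and who meet the eligibility criteria; 190 are to be enrolled.
- **Last visit (II, Data Collection Overview).** "12 months Post-op (± 90 days"), which is day 275 to day 455. Under IX.D.8, participation is expected to end with that visit.
- **Revision (IX.D.3).** A subject who has a study component removed because of a complication, even one screw of three, gets an adverse event report and a study completion form, and leaves the study.
- **Late consent (V and VI).** Patients already treated with the device "may be enrolled in the study if informed consent occurs prior to the end of the 6 weeks follow-up visit window".

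**The concern.** A percentage estimates a 12-month risk cleanly only if every subject in the denominator is observed to 12 months or to the event. Here one in five is expected to be lost, and event-free subjects may be last seen up to 90 days before the horizon.

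Sections VI and XI.B point to different denominators. Dividing by everyone enrolled treats lost subjects as event-free and reads low. Dividing by completers plus events keeps the events of subjects later lost but drops lost subjects without an event, and reads high. A third reading of evaluable at 12 months, taken literally, would leave out subjects terminated at device removal, although implant removal before healing is itself a primary event under IV.

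The study has no concurrent arm to share the bias. The result is to be set against about 15%, and XI.B sizes the study to show an improvement on that figure. If the denominator is chosen after the data are seen, that choice can settle the comparison.

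**Working it through.** **1. The plan's own figure.** Alpha, power and test are not stated. With a one-sample proportion test, two-sided 0.05 and 80% power (assumed):

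n = [(1.96 × √(0.15 × 0.85) + 0.8416 × √(0.075 × 0.925)) / (0.15 − 0.075)]² = [(0.6998 + 0.2217) / 0.075]² = 150.97, so 151.

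151 / 0.8 = 188.75, or 189, against 190 stated. Both figures reproduce and neither is disputed. Dividing by 0.8 fits a reading in which the 151 are those who remain after loss.

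**2. Assumptions for the bias calculation (not in the documents).** Loss of 20%, unrelated to reoperation risk, uniform over days 0-365. No deaths. Events counted to day 365. Last visits either uniform over days 275-455 or all at day 365. Event time F(t) = 1 − exp[ln(1 − p) × (t/365)^k], with k = 1 (constant hazard) or k = 0.5 (front-loaded).

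**3. Expected percentages.** Let A be the mean of F at the earlier of last visit and day 365, and B the mean of F up to loss among those lost.

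- All enrolled: E = 0.8A + 0.2B.
- Completers plus events: E / (E + C), where C is the event-free share seen at the final visit.

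Example with p = 0.075, k = 1 and all visits at day 365: A = 0.0750 and B = 0.0380, so E = 0.0600 + 0.0076 = 0.0676. C = 0.8 × 0.925 = 0.740, and 0.0676 / 0.8076 = 0.0837.

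| True risk | Last visits | All enrolled (k = 1; 0.5) | Completers plus events (k = 1; 0.5) |
|---|---|---|---|
| 7.5% | uniform 275-455 | 6.39; 6.82 | 7.81; 8.30 |
| 7.5% | all at day 365 | 6.76; 7.01 | 8.37; 8.65 |
| 15% | uniform 275-455 | 12.84; 13.67 | 15.54; 16.46 |
| 15% | all at day 365 | 13.54; 14.04 | 16.61; 17.11 |

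In the uniform rows, a loss dated after an early final visit counts as a completer. Coding it as lost adds 0.1-0.2 points.

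**4. Kaplan-Meier at day 365**, 1 − Π(1 − dⱼ/nⱼ), with the uniform window and 2,000,000 simulated subjects: 7.49% and 7.51% for a true 7.5%; 14.95% and 15.00% for a true 15%. In trials of 190 its SD is 2.0-2.1 points at 7.5% and 2.8-2.9 at 15%. The largest errors in the table are 8.65 − 7.5 = 1.15 points and 15 − 12.84 = 2.16 points, both below the SD.

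**5. Effect on the comparison with 15%.** Exact 95% upper limits:

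| Reoperations | Over 190 | Over 151 |
|---|---|---|
| 13 | 11.4% | 14.3% |
| 14 | 12.1% | 15.1% |
| 18 | 14.6% | 18.2% |
| 19 | 15.2% | 19.0% |

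From 14 to 18 the denominator alone decides whether the limit is below 15%. At a true 7.5% the expected number of observed events is 190 × 0.0639 to 190 × 0.0701, or 12 to 13, so this range lies close to what the plan anticipates.

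In two sets of 20,000 simulated trials of 190 (uniform window, true 7.5%), the upper limit was below 15% in 94-96% of trials over all enrolled, 67-77% over completers plus events, and 78-83% with Kaplan-Meier. The two percentages disagreed in 20-27%. At a true 15% the corresponding shares were about 5-10%, about 1% and about 2% (nominal 2.5%).

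**6. If removals were dropped.** Suppose half of reoperations are removals (assumed) and those subjects leave both numerator and denominator. A completers-plus-events rate r becomes (r/2) / (1 − r/2): 7.81-8.65% becomes 4.1-4.5%, and 15.54-17.11% becomes 8.4-9.4%.

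**7. Death.** With constant hazards λ₁ = −ln(1 − p) and λ₂ = −ln(1 − d), the competing-risk incidence is λ₁/(λ₁ + λ₂) × [1 − (1 − p)(1 − d)]. For assumed mortality d of 5%, 10% and 15%, it is 7.31%, 7.12% and 6.93% when p = 7.5%, and 14.63%, 14.26% and 13.88% when p = 15%.

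**The case against.** Several points on the other side have force.

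- **The percentage is inferred.** A reader might say that the plan prescribes a crude percentage for the primary endpoint. XI.A gives general methods only, and applying them to reoperation is an inference, although no other method is offered.
- **The denominators are not absent.** A reader might infer that the plan has none. It has two, in VI and XI.B, and they are unreconciled.
- **The window is not a further source of upward error.** For completers plus events it partly offsets the bias: 7.8-8.3% with visits spread over the window, against 8.4-8.7% with all visits at day 365.
- **Kaplan-Meier does well because independent loss was built in.** If poor recovery or surgery elsewhere drives loss, it is biased too. It also needs some follow-up to day 365: if every last visit were at day 275, it would read F(275), 5.7-6.5% for a true 7.5%.
- **The handling of death is open.** The simulations in steps 4 and 5 are for Kaplan-Meier without deaths. Making death a competing event lowers the figure (step 7), which favours the device unless the benchmark was built the same way, and the documents do not say how it was.
- **The decision rule is assumed.** XI says that descriptive summaries are the basis of reports and gives no success criterion.

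These points limit how far one estimator can be called superior. They do not supply the missing rule. A descriptive percentage still needs a denominator, and XI.B does aim to show an improvement on the historical rate.

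**Conclusion.** The concern stands in this form: the plan does not fix how incomplete follow-up enters the primary rate, and a day-365 time-to-event estimate is a better method at little cost, provided that loss is unrelated to reoperation risk. Under the assumptions in step 2, a true 7.5% reads about 6.4-7.0% or 7.8-8.7% depending on the denominator, and a true 15% about 12.8-14.0% or 15.5-17.1%.

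The average error is below the sampling SD, and its direction depends on the denominator, so the documents do not support a claim that the plan is biased for or against the device. The practical risk is that an unspecified choice decides the comparison with 15% when 14 to 18 reoperations are seen, if success is read as an exact 95% upper limit below 15%.

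A reader might also infer that subjects terminated at revision will be discarded. The documents do not say so: IX.D.3 requires the revision to be reported and the reason for exit recorded. They also do not say that these subjects are kept as events, and because that reading carries the largest error (step 6), it should be closed off explicitly. The figures of 151 and 190 are unaffected.

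**What to change.** In XI.A:

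1. Make the primary estimate the risk of reoperation by day 365 from surgery, in all eligible implanted subjects, by a time-to-event method with a 95% CI.
2. State that subjects terminated at revision under IX.D.3 count as events on the date of surgery for that event, and that others are censored at last contact.
3. Specify both Kaplan-Meier (death censored) and cumulative incidence with death as a competing event. Name one as primary before the data are seen, matched to how the benchmark of about 15% was calculated if that can be established. Report the other as sensitivity.
4. Report the crude percentage as well, with its denominator stated and evaluable defined.
5. Add a sensitivity analysis over a range of reoperation rates in lost subjects, and one that excludes or left-truncates subjects consented after surgery.

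Cost: a small amount of analysis work and an amendment to the protocol text under IX.D.9 and XIV, with IRB or EC approval if required. Sample size and visits do not change. The case report forms were not available for this review, so it should be confirmed that they capture the dates of reoperation and last contact.
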